#### **3.6.2 Subject Discontinuation or Withdrawal**

The Investigator may discontinue individual subjects from the study at any time. Subjects entering the study may withdraw at any time without penalty. The right of each test subject to withdraw from the study and the right of each test subject to privacy, confidential treatment of personal data, and protection from view by others not conducting the study will be respected at all times. The Investigator will provide a written report on the appropriate case report form including the date and reason for discontinuance.

### **3.7 Source Data**

Electronic data capture (eDC) will be used for this study. If not entered directly into eDC, data will first be recorded onto a DCS, followed by entry into the appropriate electronic case report form (eCRF). Wherever the data are entered first is considered the source document.

[REDACTED]

### **3.8 Computerized Systems**

All study data will be loaded into the [REDACTED] data management system.

The current 3M Health Care document storage system, [REDACTED] will be used to store the study documents.

[REDACTED] may be used for study documentation and data analysis.

### **3.9 Protocol Modifications**

#### **3.9.1 Protocol Amendments**

A protocol amendment is defined as a change in procedure that is identified and documented before initiation. A significant amendment means one that affects the safety, rights or welfare of subjects, the scope of the investigation or the scientific quality of the study.

All protocol amendments must be documented and approved by the Investigator and study monitor prior to implementation. All significant protocol amendments must also be pre-approved by the reviewing IRB/EC prior to implementation.

3M will submit significant protocol amendments to the Investigator for submission to the IRB/EC. 3M will also notify the Investigator when a protocol amendment may be implemented.

#### **3.9.2 Protocol Deviations**

A protocol deviation is defined as a change in procedure that has not been documented before initiation and therefore has not been reviewed and approved with the study sponsor and/or reviewing IRB/EC prior to initiation. All deviations from the study protocol are to be documented and reported to the investigator/study sponsor and reviewing IRB/EC.

A deviation is a departure from the protocol that will likely affect the safety, rights or welfare of subjects, the scope of the investigation or the scientific quality of the study.

A protocol deviation is only for an individual subject. Deviations that potentially affect 1) subject safety, rights or welfare, 2) data integrity or 3) compromise the statistical analysis of the study require immediate communication to 3M. The Investigator or designee must contact the 3M study monitor [REDACTED]. A Protocol Deviation Form must be completed by the Investigator and include the type of deviation and a description of the circumstances surrounding the deviation. A copy is sent to the 3M study monitor [REDACTED] of identifying the occurrence.

Deviations, which are made to protect the life or physical well-being of a subject in an emergency, must be reported by the Investigator to the IRB/EC within 5 working days of occurrence.

## **4. SUBJECT SELECTION**

Healthy male subjects will be recruited. A suitable number of subjects will be enrolled in the wash out (pre-inclusion), screening and treatment phase, such that a total of 18 subjects are evaluable for efficacy at completion of the study.

[REDACTED]

Subjects must follow all Subject Instructions (Appendix 14.5) and satisfy inclusion/exclusion criteria prior to enrollment into the treatment phase of the study.

All subjects will be provided verbal and written information about the study procedures, and subject instructions (Appendix 14.5). The following inclusion/exclusion criteria will be reviewed on wash out (pre-inclusion), screening and treatment day to establish eligibility for participation:

#### **4.1 Subject Inclusion Criteria**

Subjects to whom *all* of these conditions apply will be eligible for enrollment in this study:

1. Male subjects of any race who are at least 18 years of age,
2. Subjects must have a [REDACTED] area on their back region to accommodate the treatment coverage area,
3. Subjects must be in good general health,
4. Subjects who satisfy all inclusion/exclusion criteria and will voluntarily read and sign the Informed Consent Form,
5. Subjects who have good skin condition on the test sites,
6. Subjects who are willing to report to the study facility approximately 72 hours prior to Screening or Treatment Day for clipping, if needed,
7. Subjects who are willing to avoid showering and tub-bathing within 72 hours prior to Screening and Treatment Days, and
8. Subjects who have Screening Day baseline counts of  $\geq 3.00 \log_{10}$  per  $\text{cm}^2$  in each of the 3 sample sites (center, mid-peripheral and peripheral) in the treatment area (back region).

#### **4.2 Subject Exclusion Criteria**

Subjects to whom *any* of these conditions apply will be excluded from this study:

1. Participation in another clinical study in the past 30 days, current participation in another clinical study, or previous participation in this study,
2. Has taken antihistamines in the 48 hours prior to Treatment Day,
3. Any tattoos, scars, breaks in the skin, or any form of dermatitis, or other skin disorders (including acne) on the applicable test areas,
4. A history of skin allergies,
5. A history of skin cancer within 6 inches of the test areas,
6. Known sensitivity to acrylate-, chlorhexidine gluconate-, or alcohol-containing products, or to medical tape, metals, natural rubber latex, vinyl, or skin-marking inks,
7. A medical diagnosis with physical condition that may put the subject at risk, such as a current or recent severe illness, hepatitis, organ transplant, congestive heart disease, or any immunocompromised conditions, such as AIDS (or HIV positive),
8. Any medical condition or use of any medications that, in the opinion of the Investigator, should preclude participation,

9. Topical antimicrobial exposure within 14 days prior to Screening Day and throughout the study. Restrictions include, but are not limited to antimicrobial soaps, medicated shampoos, medicated lotions, antiperspirants/deodorants, perfumes, after shaves, and colognes,
10. Use of systemic or topical antibiotic medications, steroid medications, or any other product known to affect the normal microbial flora of the skin within 14 days prior to Screening Day and throughout the study,
11. Exposure of the test areas to solvents, acids, bases, strong detergents, fabric softener-treated clothing, or other household chemicals within 14 days prior to Screening Day and throughout the study,
12. Swimming in chemically treated pools or bathing in hot tubs, spas, or whirlpools within 14 days prior to Screening Day and throughout the study,
13. Use of tanning beds, hot waxes, or depilatories (in the applicable test areas) within 14 days prior to Screening Day and throughout the study
14. Bathing and showering within 72 hours prior to Screening Day and throughout the study, or
15. Subject has used moisturizers or any topical treatment (e.g. lotion, sunscreen or shaving cream) on the test sites in the 24-hour period prior to Screening Day and Treatment Day participation in the study.

#### **4.3 Subject Informed Consent**

The Investigator or designee must ensure that written informed consent to participate in the investigation is obtained before including any individual as a subject in the investigation. The Investigator or designee must provide the prospective subject or the representative sufficient opportunity to consider whether or not to participate, and minimize the possibility of coercion or undue influence. The process is designed to 1) give the subject all the information that they need, 2) ensure that the subject understands the information and 3) give the subject a chance to consider study participation. The process should permit the subject to ask questions and exchange information freely.

Specifically, the Investigator or designee is to explain to each subject all elements of informed consent as specified in 21 CFR 50.25 (Appendix 14.6). After the explanation, the subject or representative will voluntarily sign and date the consent form if they wish to participate in the study. A copy of the consent form must be provided to the subject. A signed and dated copy of the consent form must be maintained in the Investigator study documentation file at all times. Consent and study participation, with the date, must be documented in the subject's record.

### **5. TREATMENT OF SUBJECTS**

#### **5.1 Medication(s)/Treatment(s) Not Permitted**

Exposure of the test areas to antimicrobial agents is not permitted within 14 days prior to Screening Day and for the duration of the study. Restrictions include, but are not limited to antimicrobial soaps, antiperspirants/deodorants, shampoos, lotions, perfumes, after shaves, colognes, steroid medications and topical or systemic antibiotics.

[REDACTED]

## 5.2 Subject Compliance

Answers to the inclusion/exclusion criteria questions asked at the beginning of the Screening and Treatment Phases will determine compliance to the requirements of the study.

## 5.3 Study Procedures

These study procedures are based on ASTM E1173-15, Standard Test Method for Evaluation of Preoperative, Precatheterization, or Preinjection Skin Preparations.

### 5.3.1 Wash Out (Pre-inclusion) Phase

Perform the Informed Consent process. After the subject has signed the informed consent form assign the subject a screening number and complete the Inclusion/Exclusion form.

If the inclusion/exclusion criteria are satisfied, prior to the scheduled Screening Day, subjects will undergo a minimum 14-day wash out (pre-inclusion) phase to allow for the removal of any antimicrobial agents from the subjects' skin. Subjects are to refrain from the use of products containing antibacterial agents as written in the Subject Instructions (Appendix 14.5). Subjects will be given personal hygiene kits containing non-antimicrobial products for use during this period. Subjects will be instructed to use these products through completion of the Treatment Phase or until notified by the Investigator or designee.

In addition, subjects must avoid systemic or topical antibiotics or medications and contact with chemically treated swimming pools or hot tubs, hot waxes, and depilatories on the test area for 14-days before the scheduled Screening Day. If it becomes necessary to take systemic antibiotics or to apply topical medications to the test area within this wash out (pre-inclusion) period, the subject must contact the Investigator or designee as soon as reasonably possible so that another subject may be recruited.

If subjects require hair removal to facilitate sample collection, the subject will be asked to return to the test facility approximately 72 hours before the Screening Day. Subjects will not be allowed to shower or bathe for 72 hours prior to their scheduled screening appointment.

### 5.3.2 Screening Phase

Prior to collection of the screening baseline samples, the Investigator or a designee will complete the screening Inclusion/Exclusion form. A visual skin assessment of the test area will be performed. The test area within the back region is defined as the uppermost aspect up to the top of the scapula extending down to just above the sacrum as shown in Appendix 14.7. Using a [REDACTED] sterile template, the corners of each back test area will be marked directly on the skin using a nontoxic skin marker. Three sampling sites will be numbered within the test area. The 3 sampling sites within each back test area represent the 3 screening baseline sites (center, mid-peripheral, and peripheral). The positioning and numbering of the sampling sites are standard for all subjects (Appendix 14.7). The screening baseline samples will be collected using the cup scrub technique described in Section 6.2.1.1.

All three sampling sites (center, mid-peripheral and peripheral) on the test area (back region) must meet the screening baseline requirements stated in the inclusion criteria to be enrolled into the Treatment Phase of the study. Those subjects who qualify will be notified and will continue

to follow the instructions in Appendix 14.5 until completion of the scheduled Treatment Day. If subjects require hair removal to facilitate sample collection, the subject will be asked to return to the test facility approximately 72 hours before Treatment Day. Subjects will not be allowed to shower or bathe for 72 hours prior to Treatment Day.

### **5.3.3 Treatment Phase**

A sufficient number of subjects who meet the inclusion criteria will be enrolled into the Treatment Phase of the study, such that at least 18 treatment sites (back region) are evaluable at completion of the study.

The Investigator or a designee will complete the treatment Inclusion/Exclusion form. If these criteria are satisfied, complete information on demographics and perform a visual skin assessment to evaluate the condition of the test area.

#### **5.3.3.1 Preparation of Test Areas**

A Test Site Diagram for the test area (back region) is shown in Appendix 14.7.

The test area within the back region is defined as the uppermost aspect up to the top of the scapula extending down to just above the sacrum as shown in Appendix 14.7. Using a [REDACTED] [REDACTED] sterile template, the corners of each back test area will be marked directly on the skin using a nontoxic skin marker. Six sampling sites will be numbered within the test area. The positioning and numbering of the sampling sites are standard for all subjects (Appendix 14.7). The 6 sampling sites within each back test area represent the 3 baseline (pre-prep) sites (center, mid-peripheral, and peripheral) and the 3 post-prep sample sites (center, mid-peripheral, and peripheral). The sampling sites are designated as Site 1 baseline (pre-prep) center, Site 2 baseline (pre-prep) mid-peripheral, Site 3 baseline (pre-prep) peripheral, Site 4 (post-prep) center, Site 5 (post-prep) mid-peripheral and Site 6 (post-prep) peripheral. The three post-prep sampling sites, sites 4, 5 and 6, will be randomized as the 10-minute and 13-minute post-prep sample sites.

After the back region test area is marked and sampling sites are numbered, the 3 baseline (pre-prep) samples will be collected using the cup scrub technique described in Section 6.2.1.1.

#### **5.3.3.2 Study Product Application**

Following baseline sample collection, the test area will each be prepped with the study product.

[REDACTED]

[REDACTED]

The study product will be applied to the entire test area per the Investigational Product Application Instructions (Appendix 14.2). The duration of the prep application procedure is 30-seconds.

[REDACTED]

#### **5.3.3.3 Evaluation of Skin Irritation**

Prior to collection of the baseline and the [REDACTED] post-prep samples, the skin in each test area will be evaluated for indications of skin irritation, based on the Skin Irritation Rating Scale

[REDACTED]

[REDACTED]

(Appendix 14.8). Skin irritation ratings for each area will be recorded on the Skin Irritation Rating form. [REDACTED]

[REDACTED] Any area with a rating of 3 should not be sampled.

#### 5.3.3.4 Timing of Post-Prep Sample Collection

The 3 post-product application sample sites will be randomized so that 2 of the 3 sites will be sampled at one of the post-product application sample times (10 minutes or 13 minutes) and the third within the sample time remaining. The 3 sample locations within the prepped area will be demarcated such that each is taken from the same location on each of the subjects.

Microbial samples will be collected at 10 minutes [REDACTED] or 13 minutes [REDACTED] post-prep from the sampling sites within the test area. Post-prep timing begins upon completing the application of the study products, including the 3-minute drying time. Microbial samples will be collected using the cup scrub technique described in Section 6.2.1.1.

Following the final sample collection, residual study products will be removed from the subject's skin [REDACTED]

### 6. ASSESSMENT OF EFFICACY

#### 6.1 Efficacy Parameters

The primary measure of coverage area with efficacy [REDACTED] is measured as  $\geq 2 \log_{10}$  CFU/cm^2 reductions calculated by subtracting the  $\log_{10}$  number of microorganisms recovered at a specified sampling time following product application from the  $\log_{10}$  number of microorganisms recovered from baseline sampling. Baseline samples must satisfy the inclusion criteria,  $\geq 3.0 \log_{10}$  CFU/cm^2 in each of the 3 sampling sites, to be used in data analysis.

#### 6.2 Assessment Methods

##### 6.2.1 Microbiological Methods

###### 6.2.1.1 Sample Collection and Processing

Quantitative cultures will be obtained from sampling sites using a modification of the cup scrub method of Williamson and Kligman.

[REDACTED]

A sterile scrub cup will be placed and held firmly on each site. **Scrub 1:** [REDACTED] [REDACTED] SSS will be aseptically pipetted into the scrub cup. The skin will be scrubbed in a circular motion with moderate pressure for 1 minute using a sterile policeman. Using a sterile transfer pipette, the scrub solution will be transferred to a sterile collection tube. **Scrub 2:** [REDACTED] [REDACTED] fresh SSS will be pipetted into the scrub cup and the scrub procedure will be [REDACTED]

[REDACTED]

repeated. This solution will be pooled with the solution from Scrub 1 for a total sample volume of approximately 6 mL per site.

Following collection, each sample tube will be capped tightly [REDACTED] followed by [REDACTED] 30-second vortex. A 1.0 mL aliquot of each sample will be diluted into sterile tubes containing 9.0 mL PBW. Serial 10-fold dilutions will be performed in PBW, as appropriate. One-milliliter (1.0-mL) aliquots of selected dilutions will be pour-plated in duplicate using TSA+N. **Samples must be plated within 30 minutes of collection.** [REDACTED] After 72 [REDACTED] hours of aerobic incubation at  $30 \pm 2^{\circ}\text{C}$ , colonies will be counted and viable cells in the original sample will be calculated using standard methods. [REDACTED]

#### **6.2.1.2 Collection of Raw Data**

Raw colony counts from each of the dilutions will be recorded on the appropriate data collection sheet (DCS) for each subject.

#### **6.2.1.3 Neutralization of Investigational Products**

Prior to Treatment Day the effectiveness of the neutralizers contained in the microbial sampling solution will be tested based on ASTM E1054-08 (2013), Standard Test Methods for Evaluation of Inactivators of Antimicrobial Agents. The protocol for neutralization validation is provided in Appendix 14.9.

### **6.3 Subject Discontinuation**

The Investigator or designee may discontinue individual subjects from the study at any time. Subjects may voluntarily withdraw from the study at any time. The Investigator or designee will provide a written report on the appropriate form including the date and reason for discontinuation. Subjects who have been previously screened may not be re-entered into the study.

## **7. ASSESSMENT OF SAFETY**

### **7.1 Safety Parameters**

The principal measure of safety will be the incidence of adverse events reported during the study and a summary of the skin irritation rating scores. [REDACTED]

### **7.2 Assessment Methods**

The Investigator or designee will assess the subject's skin condition prior to collection of the baseline and post-prep (10-minutes or 13-minutes) samples using the Skin Irritation Rating Scale (Appendix 14.8).

### **7.3 Adverse Events**

The Investigator is responsible for identifying adverse events that occur to each subject. An adverse event can be identified by the Investigator or reported by the subject.

**Definitions:**

- Adverse event (AE) means any undesirable clinical occurrence in a subject whether or not it is considered to be drug related.
- Drug-related adverse event (ie, adverse drug experience) is an adverse event that is considered by the Investigator to have a reasonable likelihood of being associated with the investigational drug.
- Life-threatening adverse drug experience is any adverse drug experience that places the subject, in the view of the Investigator, at immediate risk of death from the reaction as it occurred (does not include a reaction that, had it occurred in a more severe form, might have caused death).
- Serious adverse drug experience is an adverse drug experience that is fatal or life-threatening, is permanently or significantly disabling/incapacitating, requires inpatient hospitalization or prolongation of existing hospitalization, or results in a congenital anomaly/birth defect.
- Unexpected adverse drug experience is one not previously identified in nature, severity or frequency of incidence in the current Investigator brochure, in the clinical plan, or elsewhere in the current IND application and amendments.

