**Recording and Reporting:**

The Investigator records each AE occurring in the study, including those not thought to be associated with the drug, on the Adverse Event Record. Documentation includes the AE description, severity at onset, seriousness, date of onset and resolution, relationship to the investigational drug, action taken, and outcomes.

The Investigator must promptly report all adverse drug experiences to the 3M study monitor. If the adverse drug experience is also considered by the Investigator to be serious and/or unexpected the Investigator must report it to the IRB/EC as soon as possible.

3M reports (by telephone or fax) a death or life-threatening adverse drug experience to the FDA within 7 days of notification, and submits a follow-up report within 15 days.

A serious and unexpected adverse drug experience involving a non-3M commercialized product is reported to the 3M study monitor and IRB/EC.

If a subject does not experience an AE during the study, the absence of such must be recorded on the form.

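### The closed definition of a serious adverse drug experience in Section 7.3 leaves out a product reaction that needed urgent intervention to avert a listed outcome but ended without admission

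*Combined protocol and SAP*

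**What the plan says.** Section 7.3, Definitions, sets out the seriousness rule in one sentence. It opens: "Serious adverse drug experience is an adverse drug experience that is fatal or life-threatening". It continues with permanent or significant disability or incapacity, and then an event that "requires inpatient hospitalization or prolongation of existing hospitalization, or results in a congenital anomaly/birth defect". The list ends there. It has no illustrative wording, no item left to the Investigator's judgement, and no item for an event in which treatment prevented a listed outcome.

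The same section defines life-threatening as placing the subject, in the Investigator's view, "at immediate risk of death from the reaction as it occurred". It adds that this "does not include a reaction that, had it occurred in a more severe form, might have caused death".

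Section 7.3, Recording and Reporting, makes seriousness one of the items documented for each adverse event. It then sets three routes:

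- **Sponsor's monitor:** every adverse drug experience, promptly, whatever its seriousness.
- **IRB/EC:** the rule for an adverse drug experience is that, if it is "considered by the Investigator to be serious and/or unexpected the Investigator must report it to the IRB/EC as soon as possible".
- **FDA:** "3M reports (by telephone or fax) a death or life-threatening adverse drug experience to the FDA within 7 days of notification", with a follow-up report within 15 days.

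Section 1.5 commits the study to 21 CFR 312 by name. Section 10 says that sponsor SOPs ensure reporting in compliance with the regulations cited in Section 1.5.

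**The concern.** A seriousness label should separate reactions that came close to a grave outcome from trivial ones. Under Section 7.3 a reaction that was stopped by prompt treatment, and ended without admission, gets the same label as mild redness. One example is an acute allergic reaction, judged not to carry immediate risk of death, that is treated on site or in an emergency department and sent home.

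The scenario is relevant to this product. Exclusion 6 in Section 4.2 removes people with "Known sensitivity to acrylate-, chlorhexidine gluconate-, or alcohol-containing products", and Section 1.1 names chlorhexidine gluconate and isopropyl alcohol as ingredients. That exclusion reaches only known sensitivity; a first reaction can still occur.

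At stake is how a reaction in a healthy volunteer is classified and, for a narrow group of reactions, whether Section 7.3 sends it to the ethics committee. The point concerns events judged drug-related, because that is all the definition covers.

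**Working it through.** No arithmetic applies: the plan states no figure here, and the point depends on no rate, margin or sample size. The check takes four product-related reactions through the definitions and the three routes in Section 7.3. None of the four is fatal, and none is permanently or significantly disabling. Unexpected is read as failing to match what was previously identified in any one of nature, severity or frequency.

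| Reaction | Label | Monitor | IRB/EC | FDA step in 7.3 |
|---|---|---|---|---|
| A. Immediate risk of death; treated, not admitted | Serious | Yes | Yes | Yes |
| B. Intervention averted a listed outcome; below immediate risk of death; not admitted; unexpected | Non-serious | Yes | Yes | None stated |
| C. As B, but already identified in nature, severity and frequency | Non-serious | Yes | None | None stated |
| D. Inpatient admission; not life-threatening; unexpected | Serious | Yes | Yes | None stated |

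The rows show the following.

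1. A is serious without admission, so the gap lies only below the threshold of immediate risk of death.
2. B and C meet no item on the list. The limit on life-threatening shuts out the argument that the reaction could have become worse. An Investigator who follows the text has no ground for recording either as serious.
3. All four reach the sponsor's monitor. B also reaches the IRB/EC, because that rule is triggered by unexpectedness alone. Only C has no IRB/EC step.
4. The FDA column depends on death or threat to life, not on the serious label. D is serious and still has no stated FDA step. The FDA question is therefore separate from the definition.

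Adding the intervention outcome makes B and C serious and gives C an IRB/EC step. A and D do not change, and neither does any entry in the FDA column.

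The definitions and reporting paragraphs of Section 7.3 carry no redaction marks, so blacked-out text does not explain the omission.

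**The case against.** The strongest objection is that the documents contain no second definition of seriousness for this one to contradict. Section 1.5 cites 21 CFR 312 by name only. On the documents alone, the narrow list is a drafting choice and cannot be shown to be an error. This stands, and the point is accordingly an improvement to a stated rule. The consequence for reactions B and C follows from the text all the same.

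Second, part of the example is already covered. Life-threatening is the Investigator's judgement and needs no admission, and disability need not be permanent if it is significant. Exclusion 4 in Section 4.2 also removes people with a history of skin allergies. This narrows the gap without closing it.

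Four stronger readings are tempting but not supported:

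- **That the ethics committee would be left out.** A reader might think a reaction type listed in the Investigator Brochure is automatically expected. The definition also covers severity and frequency. The brochure is not available, so whether any reaction would fall in row C is unknown.
- **That the narrow definition causes the narrow FDA step.** The FDA step does not use the serious label.
- **That Section 7.3 exempts other serious and unexpected reactions from FDA reporting.** It is silent on them. Sections 1.5 and 10 already bind the sponsor to 21 CFR 312 and to SOPs for compliant reporting.
- **That the gap can be sized by confidence bounds on a serious-event rate.** The visible text plans no such analysis, and any event entered would be hypothetical. The adverse event summary in Section 8.2.2 is partly redacted.

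**Conclusion.** The point holds in a limited form. By stated rule, a drug-related reaction must be recorded as non-serious when it needed urgent intervention to prevent a listed outcome but stayed below immediate risk of death, was not significantly disabling and was not admitted. The sponsor's monitor still receives it, and so does the IRB/EC if it is unexpected in any of the three respects. The routing gap is confined to fully expected reactions.

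The size is small and cannot be put as a number. The principal safety measure in Section 7.1 includes adverse event incidence, which counts the event under either label. Efficacy and sample size are untouched.

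The conclusion assumes that the outcome list is read as closed, as written, and that the seriousness entry follows the protocol's definition; the Adverse Event Record itself is not visible. The FDA wording is a secondary clarification and not an error by itself. The case for changing the definition rests on its low cost and clearer classification in healthy volunteers, who by Section 1.3 gain no direct health benefit.

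**What to change.** **Main change, Section 7.3, Definitions.** Add one outcome to the serious definition: *or that, in the Investigator's judgement, required medical or surgical intervention to prevent one of the outcomes listed here.* If the Adverse Event Record lists the criteria, add the matching option.

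**Secondary clarification, Section 7.3, Recording and Reporting.** State what the sponsor does with an adverse drug experience that is both serious and unexpected but neither fatal nor life-threatening, on the timing set by its IND obligations, so that the section agrees with the 21 CFR 312 commitment in Section 1.5. This is a separate edit, because the first one does not alter the FDA step.

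**Cost.** Two sentences and possibly one form entry. The downside is that a few more events may be labelled serious. No study procedure, sample or analysis changes.
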